4.1.2 Treatment period

Description of Part A Study Arms

For Arms A1 and A2: DLT evaluable patients were enrolled in the dose-escalation Part A of this study. At the time of protocol amendment 5, the MTDs/RP2D for each of the 2 agents in combination with MEDI4736 (durvalumab) had been identified [[AstraZeneca 2016 \(a\)](#), [AstraZeneca 2016 \(b\)](#)]. In addition, the Arm A3 dose of AZD5069 80 mg twice daily (BID) with alternate dosing schedule was determined to be safe and tolerable. All additional cohorts of Part A enrolled (Arms A4 and A6) patients with advanced solid malignancies refractory to standard therapy or for which no standard of care regimen currently exists. Patients were allocated to treatment in both parts of the study after first considering their history, and any anticipated need to use herbal supplements and/or foods prohibited with concurrent administration of AZD5069. A 14 day washout period will be required for patients who have previously been receiving preparations not compatible with AZD5069. Based on the criteria detailed in Section 3.8.2 the Investigator will then assess whether the patient may be allocated to treatment with AZD5069.

Patients thus excluded by the Investigator from treatment with AZD5069 are allocated to:

- Treatment arm, A4 or A6: AZD9150 in combination with MEDI4736 or MEDI4736/tremelimumab.

Patients thus included by the Investigator for treatment with AZD5069 will be allocated to one of the following treatment arms:

- Treatment arm A4 or A6: AZD9150 in combination with MEDI4736 or MEDI4736/tremelimumab, or
- Treatment arm A3: AZD5069 in combination with MEDI4736.

The starting doses and additional dose levels chosen for each agent in this study are based on the clinical experience with each agent as monotherapy in previous trials and from Arms A1 and A2 of the dose-escalation phase of this trial. Following a 7-day lead-in period, each treatment cycle will span 28 days.

Dosing details of Part A study arms

AZD9150 Arms

For all AZD9150 arms, 3 doses of oligonucleotide are initially administered every other day during a 1-week lead-in period (Day -7 to Day -1). Subsequent cycles of dosing with the addition of antibody drugs (MEDI4736 or tremelimumab) in combination with AZD9150 will begin on Day 1 after the lead-in as described below:

Arm A1: On Day 1 after the lead-in, AZD9150 was administered at a starting dose of 2 mg/kg (IBW) Q1W via a 1-hour IV infusion, followed at least 30 minutes later on the same day by MEDI4736 20 mg/kg IV. AZD9150 was subsequently dosed Q1W, while MEDI4736 was administered every 4 weeks (Q4W). An additional dose level of AZD9150 (3 mg/kg of IBW IV Q1W) was evaluated and determined as RP2D.

Arm A4: For the AZD9150 with MEDI4736 and tremelimumab combination, beginning on Day 1 after the lead-in, AZD9150 will be administered first at 3 mg/kg IV over 1 hour (± 10 minutes). The tremelimumab infusion at 1 mg/kg IV will start approximately 1 hour after the end of infusion for AZD9150 and will be administered over approximately 1 hour. One hour after the end of infusion of tremelimumab, MEDI4736 will be infused at 20 mg/kg over a period of 1 hour (± 10 minutes). Tremelimumab will be given Q4W for a total of 4 months (up to 4 doses). MEDI4736 and AZD9150 dosing will continue Q4W throughout patient participation in the study. Therefore, the first dose of AZD9150/MEDI4736 (without tremelimumab) will be given 4 weeks after the last dose of tremelimumab.

Arm A6: Upon completion of the lead-in period, AZD9150 will be administered at 3 mg/kg of IBW IV Q1W, in combination with MEDI4736 20 mg/kg IV Q4W as described for Arm A1 above. Again, the infusion of AZD9150 should be completed 30 minutes prior to start of MEDI4736 infusion.

Ideal body weight (IBW) will be determined using the Devine formula ([Pai and Paloucek 2000](#); see Section 7.2.1). If the actual weight is less than the IBW or the patient is less than 5 feet tall, the actual weight will be used to determine the dose. During the 7-day lead-in period, AZD9150 will be administered as a loading dose on Days -7, -5, and -3. Starting with Cycle 1, AZD9150 will be administered QW on Days 1, 8, 15, and 22 of each treatment cycle.

AZD5069 Arms

For all AZD5069 arms, BID doses of appropriately sized tablets are initially administered during a 1 week lead-in period (Day -7 to Day 0). Subsequent dosing of additional antibody drugs (MEDI4736 or tremelimumab) in combination with AZD5069 will begin on Day 1 after completion of the lead-in as described below:

Arm A2: Beginning on Day 1 after the lead-in, oral/per os (PO) dosing of AZD5069 continued as before (40 mg PO BID). At least 30 minutes after the morning dose of AZD5069, MEDI4736 was administered at 20 mg/kg IV over 1 hour. Subsequent to this, AZD5069 dosing continued BID while MEDI4736 dosing was repeated Q4W. An additional dose level of AZD5069 (80 mg BID) was also evaluated in combination with MEDI4736 under the same schedule.

Arm A3: AZD5069 will be initially dosed at 80 mg BID with scheduled dose holds and titrations to manage treatment-related reductions in peripheral blood neutrophil counts, as described in Section 5.5. MEDI4736 dosing at 20 mg/kg will begin on Day 1 after the lead-in period as described for Arm A2. At the time of amendment 5, the SRC evaluated the outcome of 6 evaluable patients from Arm A3 and determined that 80 mg BID using the alternate dosing schedule for managing neutropenic toxicity was safe and tolerable to be considered as RP2D. In all arms with patients receiving AZD5069, tablets should be administered either 2 hours before or 2 hours after food, with a 2 hour window. Dose should be taken on an empty stomach at approximately the same time each day. Additional dose levels may be tested if deemed necessary to characterise combination tolerability.

Conduct of Part A Study Arms (A3, A4, and A6)

Arm A3: 6 patients were initially assessed. Since these patients progressed through the DLT period with one DLT event of Grade 3 immune hepatitis deemed related to MEDI4736, an additional 6 patients will be added to confirm the dose schedule. The algorithm as determined in Figure 7 and Figure 8 will be followed. Non-evaluable patients may be replaced. In addition to determining DLT in the DLT evaluation period (see Section 5.3.4), the SRC (see Section 5.3.5) will critically review all available data pertaining to safety, tolerability, and IM as well as PK, pharmacodynamic, and anti-tumor activity before deciding on the viability of explored dose and schedule.

For Arm A4: the aim is to conduct a safety run-in of the established dose of AZD9150 and AZD5069 (from Arms A1, A2/A3) in combination with fixed dose of MEDI4736/tremelimumab in all solid tumor patients. There is no dose-escalation planned for Arm A4. If the dose is not tolerated (≥ 2 DLT) in this combination of 3 drugs then dose-reductions will be conducted as described in Figure 4, Figure 7, and Figure 8.

For Arm A6: the dose and safety confirmation cohort AZD9150 will be given in combination with MEDI4736 at established doses of AZD9150 (from Arms A1, A2/A3) in combination with a fixed dose of MEDI4736. This will be done in patients with prostate cancer and there will be no intra-patient dose escalation. If the dose is not tolerated in this combination of 2 drugs, then dose-reduction will be conducted as shown in [Figure 4](#), [Figure 7](#), and [Figure 8](#).

Potential subjects who provide written informed consent will be screened; those who are identified as eligible will be enrolled, assessed by the Investigator for treatment with AZD5069, and assigned accordingly to a treatment arm. Following a 7-day lead-in period during which only AZD9150 or AZD5069 will be administered, combination treatment with MEDI4736 and/or tremelimumab starts on Day 1 of Cycle 1. A cycle of study treatment is defined as 28 days.

Each patient will undergo assessments for safety (DLTs, AEs, vital sign measurements, clinical laboratory tests, PS, ECGs, and physical examinations) and other assessments according to the study plan (see [Section 5.2](#)).

The DLT evaluation period will be defined as the time from the first dose of AZD9150 or AZD5069 to the end of Cycle 1 (i.e., 35 days total), or until a patient experiences a DLT, whichever occurs first. For patients in treatment arm A4 (AZD9150/MEDI4736/tremelimumab), to be deemed evaluable, a patient must have received all 3 loading doses of AZD9150 during the 7-day lead-in period, and at least 3 additional doses during Cycle 1, as well as the MEDI4736 and tremelimumab infusion during the DLT evaluation period. Patients who have suffered a DLT during or before Day 35 will also be deemed evaluable. For patients in treatment arm A3 (AZD5069/MEDI4736) to be deemed evaluable, they must have received all doses during the 7-day lead-in period (i.e., 14 doses) and at least 50% of the planned doses of AZD5069.

For Arm A6, the aim is to establish, collect, and confirm safety, tolerability, and PK/pharmacodynamic relations of the RP2D/MT2D for the 2 combinations (i.e., AZD9150/MEDI4736 and AZD5069/MEDI4736) in specific tumor types of prostate cancer at established doses from Arms A1, A2, and A3. Hence, Arm A6 will not be followed for DLTs.

Treatments in Arms A3, A4, and A6 will be administered in 4-week treatment cycles until a patient: has confirmed PD with either clinical deterioration and/or no further benefit from treatment, experiences unacceptable toxicity, or discontinues for any other reason. All patients will be evaluated regularly for response to treatment according to the study plan (see [Section 5.2](#), [Table 5](#)). Study treatment will continue between the initial assessment of progression and the confirmation of progression. Patients may continue to receive study treatment beyond confirmed PD in the absence of clinical deterioration and if the Investigator is of the opinion that the patient continues to receive benefit from treatment.

After discontinuation of treatment, patients will continue to be followed for safety, subsequent anticancer therapy, and survival. EOT evaluations, including safety assessments, shall be performed as soon as possible following the decision to discontinue treatment. Safety follow-up for IM will continue for all patients for 90 days (± 7 days) after the last dose of MEDI4736 or until the initiation of subsequent anticancer therapy. Patients who discontinue treatment for reasons other than PD will continue to undergo tumor assessments every 2 months (± 7 days) until PD is noted. All patients will be followed for subsequent anticancer therapy every 2 months (± 7 days) and for OS every 2 months (± 7 days) from the date of randomisation to the date of death due to any cause, assessed for approximately 40 months. The patients will be censored on the date of last follow-up visit. [Figure 3](#) depicts the study scheme.

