In addition, it was initially planned to demonstrate the absence of a food effect on AZD5069 absorption enrolling approximately 10 patients either in a fasted or following a high fat meal. Sponsor decision is to not open the cohort for enrolment based on data analysed for combination of AZD5069 and MEDI4736.

In summary, the status of all Part A arms conducted at study sites in the United States at the time of protocol amendment 7 were as follows:

- Treatment arm A1: enrolled 2 cohorts of AZD9150 (2 mg/kg and 3 mg/kg) every week (QW) respectively in combination with MEDI4736 (20 mg/kg every 4 weeks [Q4W]). Cohort is closed to enrolment.
- Treatment arm A2: enrolled 2 cohorts of AZD5069 (40 mg BID capsules/tablet and 80 mg tablet BID) respectively in combination with MEDI4736 (20 mg/kg Q4W). Cohort is closed to enrolment.
- Treatment arm A3: AZD5069 (80 mg BID tablet) in combination with MEDI4736 (20 mg/kg Q4W) Cohort is closed to enrolment.
- Treatment arm A4: enrolled into 3 cohorts AZD9150 3 mg/kg QW +tremelimumab 1 mg/kg Q4W +MEDI4736 20 mg/kg Q4W, AZD9150 2 mg/kg QW +tremelimumab 1 mg/kg Q4W+MEDI4736 20 mg/kg Q4W and AZD9150 3 mg/kg every 2 weeks (Q2W)+tremelimumab 1mg/kg Q4W +MEDI4736 20 mg/kg Q4W. The latter 2 cohorts were opened based on observed DLT in the cohort that dosed with AZD9150 at 3 mg/kg QW. These Cohorts are closed to enrolment
- Treatment arm A5: AZD5069+MEDI4736+tremelimumab was originally planned. Sponsor portfolio decision was to not open the cohort for enrolment based on data analysed for combination of AZD5069 and MEDI4736.
- Treatment arm A6: AZD9150 3 mg/kg QW + MEDI4736 20 mg/kg Q4W was originally planned to enroll prostate and breast cancer patients. Enrolment occurred in patients with prostate cancer. Cohort is closed to enrolment.
- Treatment arm A7: AZD5069+MEDI4736 was originally planned for patients with breast and prostate cancer. Sponsor portfolio decision to not open the cohort for enrolment was based on data analysed for combination of AZD5069 and MEDI4736.

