6.9.1 Dose modifications

If a patient experiences a clinically significant and/or unacceptable toxicity with the IP, dosing will be interrupted or the dose reduced and supportive therapy administered as required. Because of the long tissue $t_{1/2}$ of AZD9150 and MEDI4736, a 21-day (unless otherwise specified) recovery period has been allowed. If the toxicity resolves or reverts to a lower CTCAE grade within 21 days of onset and the patient is showing clinical benefit, study treatment may be restarted using the rules below for dose modifications (see [Table 11](#) and [Table 12](#)).

If the toxicity does not resolve to CTCAE grade 2 (grade 1 for liver function tests) after 21 days, study treatment should be permanently discontinued (unless otherwise specified) and the patient should be followed up for safety (see [Section 4.2.3](#) for details).

A maximum of 2 dose-reductions ([Figure 4](#), [Figure 5](#), [Figure 7](#), and [Figure 8](#)) will be allowed for an individual patient. If the second dose-reduction is not tolerated, study treatment should be permanently discontinued and the patient should be followed up for safety (see [Section 4.2.3](#) for details). The lowest doses that may be administered are:

- AZD9150: 2 mg/kg IBW Q2W (200 mg Q2W for Arm B8)
- AZD5069: 20 mg BID
- MEDI4736: flat dose administration of 10 mg/kg Q4W (MEDI4736 dose-reductions are not permitted for Arm B8)
- Tremelimumab: 1 mg/kg

If a patient experiences a clinically significant and/or unacceptable toxicity at these dose levels, study treatment should be permanently discontinued and the patient should be followed up for safety (see [Section 5.9](#) for details).

Table 11 Dose modifications for toxicity (excluding liver function tests and in case of neutropenia for AZD5069 alternate dosing schedule arms)

Toxicity	Recovery	Re-dosing	Notes
Grade 3	G2 ^a ≤21 days	Restart at dose level -1	If second dose interruption, decrease to dose level -2

	G2 ^a >21 days	Discontinue study drug treatment	
Grade 4	G2 ^a ≤21 days	Restart at dose level -2	If second grade 4 toxicity, discontinue study drug treatment
	G2 ^a >21 days	Discontinue study drug treatment	

^a Patients starting with an abnormal baseline may restart when the lab/AE returns to pretreatment status. If thrombocytopenia is accompanied by bleeding, discontinue study drug treatment. Neutropenia when on AZD5069 alternate dosing schedule should be managed as in [Figure 7](#) and [Figure 8](#)
Abbreviation: G=grade.

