7.2 Dose and treatment regimens

7.2.1 Administration of AZD9150

AZD9150: Arms A1, A4, A6, B1, B3, B5, B7, and B8: Patients will receive loading dose of AZD9150 (Days -7, -5, and -3) at the defined dose in each treatment arm as described in the study design. Following loading dose, patients will receive QW dosing of AZD9150 (except in Cohort 2 of Arm A4, and Arm B8 where the schedule of AZD9150 is Q2W). AZD9150 will be administered as a 1-hour (\pm 10 minutes) infusion. In all cases, infusion of AZD9150 is planned to be completed at least 30 minutes (in subsequent cycles if no infusion reaction in first cycle) before the start of the MEDI4736 infusion on days that both drugs are administered.

For Arm A4 specifically, the sequence of dosing for first 4 cycles would be AZD9150 infused over 1 hour (\pm 10 minutes), followed by tremelimumab infused over 1 hour (\pm 10 minutes) followed by MEDI4736 infused over 1 hour (\pm 10 minutes). Ideal body weight will be used to calculate the administered dose in all arms where AZD9150 is to be infused except Arm B8 where flat dose AZD9150 is to be administered, i.e. 200 mg as lead-in doses on Days -7, -5, and -1 and 400 mg Q2W thereafter in a 28-day cycle.

AZD9150 will be administered on an mg/kg IBW basis via a 1-hour IV infusion (a window of \pm 10 minutes will be allowed). However, the patients allocated in B8 will be administered on a flat dosing regimen. As described in Section 1, the infusion time for AZD9150 has been shortened from 3 hours in previous studies to a 1 hour infusion. The SRC will continue to monitor patients dosed with AZD9150 for any toxicities possibly associated with the shortened infusion time and may recommend modifying the length of infusion if any toxicities associated with C_{max} are observed.

Ideal body weight is used for the administration of AZD9150 as the apparent volume of distribution for oligonucleotides does not increase proportionately to body weight in obese patients or patients who weigh substantially less than their IBW (Dorr et al 1999). Ideal body weight will be determined using the Devine formula (Pai and Paloucek 2000):

$$\begin{aligned} \text{Men (kg)} &= 50 + 2.3 \text{kg} * \text{inch over 5 feet} \\ &= 50 + 2.3 \text{kg} * ((\text{actual height (cm)} - 152.4) * 0.4) \\ \text{Women (kg)} &= 45.5 + 2.3 \text{kg} * \text{inch over 5 feet} \\ &= 45.5 + 2.3 \text{kg} * ((\text{actual height (cm)} - 152.4) * 0.4) \end{aligned}$$

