7.7.5 Definition of dose-limiting toxicity evaluable patient

For patients in treatment arms A1 and A4 (AZD9150/MEDI4736 or AZD9150/MEDI4736/tremelimumab), to be deemed evaluable for dose-escalation purposes, a patient must have received all 3 loading doses of AZD9150 during the 7-day lead-in period and at least 3 additional doses during Cycle 1 as well as the MEDI4736 and tremelimumab infusion during the DLT Evaluation period or have suffered a DLT within the first 35 days of treatment.

For patients in treatment arm A2 or A3 (AZD5069/MEDI4736 or AZD5069/MEDI4736/tremelimumab), to be deemed evaluable for dose-escalation purposes, a patient must have received all doses during the 7-day lead-in period (i.e., 14 doses) and at least 42 additional doses of AZD5069 or 50% of planned doses during the DLT Evaluation period) as well as the MEDI4736 infusion and remained active on trial at the end of Day 35 of the study.

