## Statistical Analysis Plan

### 6.2. KEY DEFINITIONS

For the purposes of this study, the term “study drug” is restricted to AZD9056, AZD9150, MEDI4736, treme, and the 4 drug combinations, AZD9056/MEDI4736, AZD9150/MEDI4736, AZD9056/MEDI4736/treme and AZD9150/MEDI4736/treme.

Study Day is the day relative to the date of the first dose of study drug in Cycle 1. If a date falls on or after the date of the first dose in Cycle 1, then the corresponding Study Day is calculated as (Study date) – (Date of first dose in Cycle 1) + 1. If a date falls before the date of first dose in Cycle 1, the corresponding Study Day is calculated as (Study date) – (Date of first dose in Cycle 1). Day -1 is the day immediately before the date of the first dose in Cycle 1.

The last dose date is defined as the last non-missing date where a non-zero dose of study drug was recorded. For patients who are ongoing at the time of an interim analysis, the last dose date will be considered the date of the most recent study visit in the database for that patient where a non-zero dose of study drug was recorded.

Unless otherwise specified, baseline is the last non-missing observation before the start of study treatment in Cycle 1.

In treatment arm A1 (AZD9150/MEDI4736), A4 (AZD9150/MEDI4736 or AZD9150/MEDI4736/treme) in dose escalation Part A, an evaluable patient must have received all 3 loading doses of AZD9150 during the 7-day Lead-in period and at least 3 additional doses during Cycle 1 as well as the MEDI4736 and treme infusion during the DLT Evaluation period or have suffered a DLT within the first 35 days of treatment. In treatment arm A2 (AZD5069/MEDI4736) in dose escalation Part A, an evaluable patient must have received all doses during the 7-day Lead-in period (i.e., 14 doses) and at least 42 additional doses as well as the MEDI4736 infusion during the DLT Evaluation period or have suffered a DLT during or before the first 35 days of treatment.

An efficacy evaluable patient is defined as a patient with unidimensional measurable disease at baseline as per the RECIST version 1.1 criteria who received at least 1 dose of study treatment.

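### Arm A4: no DLT-free patient in the 3 mg/kg Q2W cohort can meet the DLT-evaluability rule of at least 3 AZD9150 doses in Cycle 1

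*Protocol*

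**What the plan says.** **Evaluability.** Three places define a DLT-evaluable A4 patient, each starting from the three lead-in loading doses. Protocol 4.1.2 adds "at least 3 additional doses during Cycle 1, as well as the MEDI4736 and tremelimumab infusion during the DLT evaluation period". Protocol 7.7.5 adds "at least 3 additional doses during Cycle 1 as well as the MEDI4736 and tremelimumab infusion during the DLT Evaluation period". SAP 6.2 adds "at least 3 additional doses during Cycle 1 as well as the MEDI4736 and treme infusion during the DLT Evaluation period". In all three, a patient with a DLT inside the 35-day window also counts. The two antibody infusions are listed in addition to the AZD9150 doses, so they cannot supply the third dose.

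**The cohorts.** The Part A arm summary in the protocol synopsis lists three A4 cohorts: AZD9150 at 3 mg/kg QW, at 2 mg/kg QW, and "AZD9150 3 mg/kg every 2 weeks (Q2W)+tremelimumab 1mg/kg Q4W +MEDI4736 20 mg/kg Q4W". SAP 3.4.1 lists the same three. Protocol 7.2.1 gives weekly dosing after the loading doses, "except in Cohort 2 of Arm A4, and Arm B8 where the schedule of AZD9150 is Q2W".

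**Use of evaluable patients.** Protocol 7.7.4 requires at least 6 evaluable patients to determine an MTD. Protocol 2.1 and SAP 4.5.1 base the Part A MTD on patients who completed the DLT evaluation.

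**The A4 dosing sentence.** The Arm A4 paragraph of Protocol 4.1.2 states: "MEDI4736 and AZD9150 dosing will continue Q4W throughout patient participation in the study". Slightly later the same section says: "Starting with Cycle 1, AZD9150 will be administered QW on Days 1, 8, 15, and 22 of each treatment cycle".

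**The concern.** The evaluability rule fits a weekly schedule. It asks for three of the four doses planned in Cycle 1 and so tolerates one missed dose. Applied to a fortnightly schedule, it asks for more doses than the plan provides. A fully compliant Q2W patient who finishes the window without a DLT is non-evaluable, while a patient with a DLT is evaluable. Evaluability then depends entirely on the outcome it is meant to measure.

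The synopsis says the two reduced-regimen cohorts were opened because of a DLT in the 3 mg/kg QW cohort. The rule therefore fails in one of the cohorts meant to show whether a lighter regimen is tolerable. Any statement for that cohort that uses evaluable patients as its denominator, including an MTD or recommended dose for the triplet, would be uninformative or impossible.

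The Q4W dosing sentence is a separate, lesser matter. It assigns AZD9150 an interval that no A4 cohort has.

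**Working it through.** **Inputs**
- Cycle length: 28 days (Protocol 4.1.2).
- DLT window: 35 days, from the first lead-in dose to the end of Cycle 1 (Protocol 4.1.2 and 7.7.3).
- Minimum AZD9150 doses in Cycle 1: 3 (Protocol 4.1.2, 7.7.5; SAP 6.2).
- AZD9150 dosing window: ±2 days (Protocol 7.2.1).
- A4 tolerability trigger: 2 or more DLTs means not tolerated (Protocol 4.1.2).
- Evaluable patients required for an MTD: 6 (Protocol 7.7.4).

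**Step 1: the plan's own figure.** Lead-in Days -7 to -1 are 7 days and Cycle 1 is 28 days. 7 + 28 = 35 days, as stated.

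**Step 2: planned Cycle 1 doses.**

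| Schedule | Count | Dosing days | At least 3? |
|---|---|---|---|
| QW | 28/7 = 4 | 1, 8, 15, 22 | Yes |
| Q2W | 28/14 = 2 | 1, 15 | No |

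**Step 3: the dosing window.** The third Q2W dose falls on 15 + 14 = Day 29, which is Cycle 2 Day 1. With the ±2-day window it could be given on calendar Day 27. It would still be the Cycle 2 Day 1 dose, not an extra Cycle 1 dose.

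**Step 4: who is evaluable.** Let d be the number of Q2W patients with a DLT inside the window. No DLT-free patient qualifies, so the number evaluable is d. The DLT proportion among evaluable patients is d/d = 100% if d is at least 1, and 0/0 if d = 0. The true DLT rate does not enter.

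**Step 5: against the MTD requirement.** A cohort tolerated under the A4 trigger has d = 0 or 1, so at most 1 patient is evaluable. Six are required. The shortfall is at least 6 - 1 = 5, whatever the cohort size.

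**Step 6: scaling the rule.** The QW rule requires 3/4 = 75% of planned doses. For Q2W, 0.75 × 2 = 1.5, which rounds up to 2 of 2, or 100%.

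**The dosing sentence, by comparison of text.** The sentence gives Q4W. The synopsis, SAP 3.4.1 and Protocol 7.2.1 give QW, or Q2W for one A4 cohort. Protocol 4.1.2 itself gives QW. No A4 cohort is described anywhere with AZD9150 at Q4W.

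**The case against.** The strongest reply is that little depends on evaluability in A4.
- The synopsis statistical section describes A4 as a small arm meant to gather and confirm safety information. Protocol 1.2 restricts the triplets to Part A, so no Part B dose rests on an A4 MTD.
- Protocol 7.7.5 defines evaluability for dose-escalation purposes, and Protocol 4.1.2 and 7.7.1 plan no escalation in A4. The A4 decision rule in 4.1.2 is a DLT count.
- SAP Section 11 centres MTD determination on the two doublets. SAP Table 2 has no DLT-evaluable set, and SAP Table 3 places DLTs on the Safety set.
- The arm is closed to enrolment.

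All of this stands, and it limits the consequence. It does not remove the defect. Protocol 4.1.2 states the A4 rule without the dose-escalation qualifier. Protocol 2.1 and 7.7.7 include the tremelimumab combinations in the MTD or recommended-dose objective, and Protocol 8.2.1 gives MTD/RP2D confirmation among the reasons for these sample sizes. The Safety Review Committee's case-by-case discretion in Protocol 7.7.6 concerns patients started in error who already meet the evaluability criteria. It gives no waiver for patients who cannot meet them. For the alternative AZD5069 schedule in Arm A3, Protocol 4.1.2 uses a share of planned doses. The Q2W cohort has no equivalent.

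A reader might also infer from the Q4W sentence that A4 patients were under-dosed. The documents do not support that. The sentence following it concerns the first visit after tremelimumab stops, which makes a drafting slip the likely explanation, and nothing shows that anyone was dosed Q4W.

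**Conclusion.** The point holds as a rule that gives the wrong result when followed. In the A4 3 mg/kg Q2W cohort, the evaluable patients are exactly those with a DLT. Their DLT proportion is 100% or undefined, and a tolerated cohort supplies at most 1 of the 6 evaluable patients needed for an MTD.

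The reach is narrow: any evaluable-patient, MTD or recommended-dose statement for that one closed cohort. The Safety-set DLT tables, the trigger of at least 2 DLTs, and the CRM for the doublets are unaffected. A reader might infer that the Part A primary endpoint as a whole, or the dose taken into Part B, is compromised. The documents do not support that, because those rest on the doublet arms.

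The conclusion assumes that the rule is read literally and that the Q2W cohort followed Days 1 and 15. Protocol Table 3 and Figure 4 could not be checked. The committee's remit is a separate document, so how it treated this cohort in practice is unknown.

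The Q4W sentence is a secondary text error with no shown effect.

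**What to change.** 1. In SAP 6.2, and in Protocol 4.1.2 and 7.7.5 if they are reissued, add a line for the A4 3 mg/kg Q2W cohort. A patient is evaluable after all three loading doses, both planned Cycle 1 AZD9150 doses (Days 1 and 15) and the MEDI4736 and tremelimumab infusions, or after a DLT within 35 days. State that this is a choice: 2 of 2 is stricter than the 3 of 4 asked of weekly patients, because 75% of two doses rounds up, and a single missed dose makes a DLT-free patient non-evaluable.
2. Record the change in SAP Section 13. The arm is closed, so this is a retrospective clarification and should be labelled as one.
3. Editorial: reword the A4 sentence in Protocol 4.1.2 so that MEDI4736 continues Q4W and AZD9150 continues on the assigned cohort schedule (QW or Q2W).

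The cost is one definition line, one entry in SAP Section 13 and one corrected sentence. No new data are needed and enrolment does not change. Only the count of DLT-evaluable patients in the Q2W cohort is affected.
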